6.4.1 Inclusion of Women and Minorities

Both men and women are eligible. Members of all races and ethnic groups are eligible for this trial.

6.4.2 Registration Procedures & Screen Failures

Initial eligibility will be confirmed by the study coordinator. The PI, Co-PI or other engaged study investigator will review and sign an eligibility checklist to confirm the patient is eligible to participate on study. All enrolled subjects will be given a unique study specific patient identification and registered through the Siteman Cancer Center OnCore database at Washington University. Screen failures are those subjects who consent to and undergo any study related procedures. A subject who signs consent in clinic but declines to participate after further discussion of the imaging protocol and study requirements with the study coordinator is not considered a screen failure and will not be registered to the protocol since no study procedures took place.

6.5.0 METHODS

6.5.1 Study Design

A single center, open-label, baseline-controlled diagnostic imaging study designed to assess the diagnostic quality and CCR2 expression detectability of ^{64}Cu -DOTA-ECL1i imaging with PET/CT. In addition, data will be collected to build the ongoing safety profile of ^{64}Cu -DOTA-ECL1i and uptake will be correlated to in vitro assays of chemokines receptor from clinically obtained biopsy/surgical specimen.

6.5.2 Patient Population

Twenty adult individuals with new diagnosis of squamous cell of the head and neck cancer who are scheduled for definitive therapy (surgery for fresh tissue collection or other standard of care therapy who have adequate tissue from tumor biopsy for analysis of CCR2) and have not received treatment for their cancer will be studied. Written informed consent will be obtained prior to the PET imaging session. ^{64}Cu -DOTA-ECL1i-PET/CT imaging consisting of a dynamic scan centered at the level of the known tumor followed by a limited body scan of the head/neck and upper chest will be performed in each patient. ^{64}Cu -DOTA-ECL1i-PET/CT images will also be correlated with all available imaging studies to assess lesion localization.

To aid prospective tissue analysis a total of 20 samples (10 each: HPV+ and HPV-) will be obtained from the Department of Pathology at Washington University and immunohistochemical staining of CCR2 will be performed.

6.5.3 PET Imaging

All subjects will have a minimum of 24 hours to review the consent form before agreeing to participate in this research project. All PET imaging will be performed with a PET/CT scanner with preference given to scanners located in the Center for Clinical Imaging Research Center (CCIR) located on the 10th floor West Pavilion of Barnes-Jewish Hospital.

All patients will undergo routine clinical staging as dictated by the treating physician. The results of ⁶⁴Cu-DOTA-ECL1i-PET/CT will not be provided to the patient or the treating oncologist/surgeon unless, in the judgment of the principal investigator, the images demonstrate an unsuspected abnormality that may warrant further evaluation.

Serum Stability and Metabolite Analysis (whenever possible): ⁶⁴Cu-DOTA-ECL1i has been shown to be stable up to 60 min in preclinical studies. Our preclinical studies showed 95% of the tracer was intact after 1 hour incubation with mouse serum. In order to assess serum stability and for metabolite analysis of ⁶⁴Cu-DOTA-ECL1i in this patient population, 2 venous samples (approximately 1 mL each) will be obtained (1 within the first 5 min of imaging and 1 at the completion of the first hour of imaging). Additional blood samples may be obtained based on results of the 2 samples to increase the time points, if necessary.

For each PET/CT study, when collected, high performance liquid chromatography (HPLC) analysis of the serum stability and metabolite profile will be performed by [name] ^{37,38}. Whole blood will be centrifuged; plasma and packed red cells will be separated and the radioactivity in each portion will be recorded. A 200 μ L aliquot of plasma will be diluted with 200 μ L MilliQ water and passed through a 0.22 micron filter prior to HPLC injection. Eluent fractions will be collected every 1 minute and analyzed by gamma counting.

6.5.3.1 PET Imaging Procedure

Following administration of 8-10 mCi of the radiotracer ⁶⁴Cu-DOTA-ECL1i-PET/CT, all twenty subjects who enter on study will undergo a 60 minute dynamic scan centered over the site of the known tumor. An additional limited scan (top of head to upper/mid-chest) will be performed approximately 1-3 hours after administration.

For dynamic imaging, the subject will be placed supine on the imaging table with arms secured comfortably by the side of the body. A low dose spiral CT scan for attenuation correction will be obtained centered on the primary tumor site. The CT will consist of a 5-20 second topogram for determining correct anatomical positioning followed by a spiral CT at a maximum of 50 mAs. Care dose will be calculated for each scan and the care dose imaging parameters will be used if less than the maximum 50 mAs is calculated. CT imaging will be acquired with a standard 120 kVp. Average spiral CT scan time is 5-30 seconds. Scans are acquired

using a 3-5 mm slice thickness. Immediately after the attenuation CT scan, subjects will be injected with 8 – 10 mCi ^{64}Cu -DOTA-ECL1i. The dose will be followed with a normal saline flush of 10-30 ml. A 60 min list mode dynamic imaging acquisition will follow study drug injection. At the end of the imaging session, subjects will be encouraged to void.

Subjects will be allowed to rest outside of the scanner until such time subject indicates they are willing to start the 2nd scan (1 – 3 hours post injection). Scan #2 will consist of a limited body scan from the vertex to upper/mid chest region. Following topogram and low dose CT scan for attenuation correction (maximum 50 mAs with care dose imaging parameters) a 2 bed limited scan from vertex to upper / mid chest will be obtained at 3-5 minutes per bed position.

To add to the existing safety profile of ^{64}Cu -DOTA-ECL1i, all subjects will undergo vital sign measurement, clinical laboratory testing, and ECG testing as specified in sections 6.5.5, 6.5.6 and 6.5.7 of the protocol.

6.5.4 PET Image Processing and Analysis

List mode dynamic PET images will be reconstructed using current scanner manufacturer recommendations as follows (frames x seconds) 12x10, 6x30, and 11x300. PET images will be evaluated qualitatively (graded on a five-point scale regarding the presence or absence of abnormal uptake: 1 = definitely negative; 2 = probably negative; 3 = equivocal; 4 = probably positive; and 5 = definitely positive) and then, semi-quantitatively (standardized uptake value (SUV), tumor-to-normal tissue ratio (T/N) or tumor-muscle-ratio (T/M)) with the knowledge of the location (correlating with all available imaging studies). SUV is a decay-corrected measurement of activity per volume of tissue ($\mu\text{Ci/mL}$) divided by the average activity per unit mass in the entire body. The overall PET image quality also will be graded (using 4-point scale with 1 being the worse and poor quality, not acceptable for diagnostic interpretation and 4 being good image quality, similar to routine clinical studies. PET analysis will not be performed in real time, but performed in batches or after all subjects have been enrolled, however, the images will be evaluated qualitatively for incidental findings.

The pharmacokinetic of the lesion time-activity curve using graphical analysis and tracer kinetic compartmental modeling will be determined. Classical receptor-ligand models will be employed to describe the kinetics of the tracers and different models to optimize goodness-of-fit will be evaluated. Goodness-of-fit will be judged by a nested F-test for the number of parameters, Akaike Information Criterion (AIC), and the Schwarz Criteria. 1-tissue with two kinetic rate constants and 2-tissue with 4 rate constants compartmental reversible models will be used to fit the data using the blood input function as input function. The blood time activity curve will be determined noninvasively from a large 3D ROI traced over the aorta (OR carotid artery) and corrected for metabolites per above analyses, if available. The measured lesion time-activity curves will be fitted to the 1- or 2-compartment model prediction and added to the plasma component weighted by the tissue blood fraction V_b . Best fit will be used to determine the distribution volume (DV) from the 1-tissue model (with $DV = K_1/k_2$), and we will determine the DV and the non-displaceable binding potential (BP) from the 2-tissue model (with $DV = (K_1/k_2)(1+BP)$ and $BP = k_3/k_4$). The graphical analysis using Logan and Patlak analysis to determine the volume of distribution (DV) also will be performed. We will further use both the plasma time activity curve and a reference region to determined DV and DVR, respectively with non-displaceable BP = DVR -1. A possible region of reference will be a suitably located

muscle in the same field of view as head and neck cancer. All quantitative and semi-quantitative metrics of ^{64}Cu -DOTA-ECL1i-PET/CT will be correlated with CCR2 receptor expression and binding affinity of each biopsy-proven tumor specimen.

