6.2.0 Objectives

We are planning to perform a trial with goals to evaluate tumor uptake of ^{64}Cu -DOTA-ECL1i in patients with squamous cell head and neck cancer with at least one measurable lesion of ≥ 1.5 cm. We also will correlate the tumor uptake of ^{64}Cu -DOTA-ECL1i with immunohistochemical staining for CCR2 receptors in the tumor specimens.

Study objectives:

- 6.2.1 To determine the diagnostic quality and CCR2 expression detection rate of ^{64}Cu -DOTA-ECL1i-PET/CT images.
- 6.2.2 To evaluate the relationship between ^{64}Cu -DOTA-ECL1i uptake and immunohistochemical staining for various types of chemokine receptors such as CCR2.
- 6.2.3 To assess the association of CCR2 expression and HPV status. CCR2 immunohistochemical staining in HPV+ and HPV- squamous cell cancer of the head and neck. To better assess the analysis of tissue prospectively we will retrospectively review a limited number of identified samples obtained from the Department of Pathology at Washington University (20 total samples).

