6.4.0 Inclusion Criteria/ Exclusion Criteria

Adult patients (men or women) with confirmed new diagnosis of squamous cell head and neck cancer who are being evaluated for surgical resection or definitive therapy are eligible to participate in this study.

Inclusion Criteria:

- Adult patient 18 years of age or older
- Cytology or biopsy-proven squamous cell head and neck cancer scheduled to be treated with standard of care surgery. Patients who are not surgical candidates should have adequate tissue from tumor biopsy for analysis of CCR2.
- Lesion size of at least 1.5 cm (treatment naïve)
- Able to give informed consent
- Not currently pregnant or nursing: Subject must be surgically sterile (has had a documented bilateral oophorectomy and/or documented hysterectomy), post-menopausal (cessation of menses for more than 1 year), non-lactating, or of

childbearing potential for whom a urine pregnancy test (with the test performed within the 24 hour period immediately prior to administration of ^{64}Cu -DOTA-ECL1i is negative

Exclusion Criteria:

- Patients with other invasive malignancies, with the exception of non-melanoma skin cancer, who had (or have) any evidence of the other cancer present within the last 2 years
- Unable to tolerate approximately 90 min (total time) of PET/CT imaging.

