6.7.0 Statistics

Demographic and clinical characteristics of the enrolled patients will be summarized using descriptive statistics with frequency and percentages used for categorical variables, median (25th, 75th) for ordinal variables and mean (standard deviation) for continuous variables. The diagnostic quality of images and CCR2 expression detection will be assessed qualitatively and semi-quantitatively for all participants and these measures (described above) will be summarized for a lesion using descriptive statistics. The association between ^{64}Cu -DOTA-ECL1i uptake and tissue signal intensity for CCR2 and other chemokine receptors will be evaluated using a Spearman correlation coefficient. Collection of additional data for the safety profile will not undergo formal statistical review.

The primary goal of this single center, open-label, baseline-controlled diagnostic imaging study is to assess the diagnostic quality and CCR2 expression detectability of ^{64}Cu -DOTA-ECL1i in head and neck cancer patients. The study is primarily descriptive and the sample size is based on feasibility of recruitment. However, a sample size of 20 achieves 80% power to detect a correlation of 0.61 using a two-sided hypothesis test with a significance level of 0.05.

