6.9.0 Record Keeping

It is anticipated that 20 subjects will be entered into this study. Initial review of images for quality and uptake will occur in real time with additional analysis performed in batches or after enrollment has been completed. The pathological analysis of the CCR2 will be performed after study enrollment has been completed on the standard of care specimens obtained at surgical resection or from diagnostic biopsy. Data collected to ensure the safety profile of ^{64}Cu -DOTA-ECL1i is accurate will be assessed from the time prior to study drug injection through imaging discharge.

A patient file will be kept in the Research Coordinators' suite located on the 10th floor of the Mallinckrodt Institute of Radiology in Barnes-Jewish Hospital South Campus. All digital data associated with ^{64}Cu -DOTA-ECL1i-PET/CT is maintained on the PET acquisition computer. Raw data files are backed up on password protected encrypted external hard drive(s). All imaging data may also be backed up on DVD after it has been transferred to a desktop PC. Processed data will be stored on the Principal Investigator's password protected desktop. CRF's and patient files will be stored in the study coordinators' office. Entrance to the PI's and coordinators' offices requires admission through two separate locked doors. Standard laboratory assessment (CBC + CMP) will be processed locally with results added to the subjects electronic medical record. ECG's are obtained for study purposes only and are not included in the electronic medical record.

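### The five-point uptake grade behind the detection rate is neither masked nor locked, so it can be set or revised with the tumour's location known

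*Combined protocol and SAP*

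**What the plan says.** - **Objective.** Section 6.2.0 lists as its first objective "To determine the diagnostic quality and CCR2 expression detection rate of" the tracer's PET/CT images. Section 6.7.0 says the primary goal is "to assess the diagnostic quality and CCR2 expression detectability of" the tracer in head and neck cancer.
- **Population.** Section 6.4.0 requires "Cytology or biopsy-proven squamous cell head and neck cancer" and "Lesion size of at least 1.5 cm". There are no tumour-free subjects.
- **Reading.** Section 6.5.4 has a five-point visual grade (1 definitely negative to 5 definitely positive), followed by SUV and tumour-to-normal or tumour-to-muscle ratios, "with the knowledge of the location (correlating with all available imaging studies"). It also says PET analysis is done in batches or after enrolment, not in real time, apart from a qualitative look for incidental findings.
- **Other imaging.** Section 6.5.2: "PET/CT images will also be correlated with all available imaging studies to assess lesion localization". No step of the reading is exempted.
- **Timing.** Section 6.9.0: "Initial review of images for quality and uptake will occur in real time with additional analysis performed in batches" or after enrolment.
- **Acquisition.** Under 6.5.3.1 the dynamic scan is centred on the known tumour. Scan #2 runs from the vertex to the upper or mid chest. Both have a low-dose CT.
- **Tissue.** Section 6.5.9 scores CCR2 staining from 0 (absent/faint) to 3 (strong).

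The plan does not mention masking of the reader, locking of the grade, the number of readers, or which grade counts as detected.

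**The concern.** The five-point grade is the only item in the plan that says whether uptake is present or absent, so a detection rate has to come from it. A reader who knows that tumour sits at a given spot may grade faint or equivocal activity there as positive. A grade given that way shows that some activity can be found where tumour is already known to be. It is weaker evidence that the tracer makes the lesion visible unprompted. Because every patient has tumour, no tumour-free scans exist on which over-reading would appear.

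What is at stake is the interpretation of the reported rate. The study is descriptive and tests no hypothesis about detection, so no type I error is involved. The image-quality half of the primary goal is not directly affected.

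**Working it through.** **1. The plan's own figure.** Section 6.7.0 gives 80% power for a correlation of 0.61 with n = 20, two-sided 0.05. Using Fisher's z with the Spearman variance factor 1.06:

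power = Φ(atanh(0.61) × √((20 − 3)/1.06) − 1.96) = Φ(0.709 × 4.005 − 1.96) = Φ(0.879) = 0.81.

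The figure reproduces, but it concerns the correlation of uptake with tissue staining. The plan gives no target, cut-off or interval for the detection rate, so there is no stated figure to reproduce on this point.

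**2. Does the text protect the grade?**
- In 6.5.4 the location phrase follows the semi-quantitative step. Read narrowly, it covers only that step, where location is needed to place a region of interest. Read broadly, it covers both steps.
- On the narrow reading the visual grade comes first, but nothing requires it to be recorded and closed before location is opened.
- Section 6.5.2 brings in the other imaging with no limit to one step.
- Section 6.9.0 has uptake judged in real time. Section 6.5.4 allows only a check for incidental findings at that stage. The word at odds between the two is uptake.

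On either reading, the grade can be set or changed with location known.

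**3. Size per patient.** Taking one lesion per patient, 1/20 = 5 percentage points. If 15/20 = 75% would be positive without location, and three or four equivocal reads move up, the rate becomes 18/20 = 90% or 19/20 = 95%. The share of equivocal scans, and grade 4-5 as positive, are assumptions; the documents give neither.

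**4. A wider range.** Let p be the share positive without location and s the share of the remaining reads moved to positive. Then observed rate = p + s(1 − p).

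| p | s = 0.10 | s = 0.25 | s = 0.50 |
|---|---|---|---|
| 0.40 | 0.46 | 0.55 | 0.70 |
| 0.60 | 0.64 | 0.70 | 0.80 |
| 0.80 | 0.82 | 0.85 | 0.90 |

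The shift runs from 2 points (0.80 to 0.82) to 30 points (0.40 to 0.70). Both p and s are assumed.

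**5. Could it be seen afterwards?** Exact 95% intervals are 56% to 94% for 16/20 and 68% to 99% for 18/20, so they overlap heavily. A single reported rate could not show a shift of this size. Two grades on the same patients would show it directly, as a count of changed reads.

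**6. Planned checks.** Section 6.5.4 correlates the quantitative and semi-quantitative metrics with CCR2 expression, and 6.7.0 correlates uptake with staining intensity. Neither names the five-point grade, and nothing masks the PET reader to the staining result.

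**The case against.** The strongest case on the other side has four parts.

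- **Wording of 6.5.4.** A reader might infer that the protocol declares the five-point grade to be given with location known. It does not: the phrase sits after the semi-quantitative step, and the order could even mean a first look without location. This stands. The gap is ambiguity plus the absence of masking or locking.
- **Other measures of detectability.** Section 6.7.0 assesses detection semi-quantitatively as well. SUV, tumour-to-muscle ratio and the kinetic measures show how far a lesion stands out from background without relying on a visual impression. This stands, so the grade does not carry the whole conclusion. But no cut-off turns those measures into a detection, so the rate still rests on the grade.
- **CCR2 rather than tumour.** The target is CCR2 expression in tumours whose site is known, and the relevant negatives are tumours with staining 0. A grade of 4 or 5 with staining 0 would hint at over-reading. So it would be too strong to infer that nothing in the design could expose it. However, no planned analysis makes that comparison.
- **Limits of masking.** Every reader knows there is a tumour, and the attenuation CT may show a lesion of 1.5 cm or more. This stands: masking will be partial. Asking the reader to mark the site still carries information, because the mark can be wrong.

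Two further inferences are unsupported. Section 6.9.0 does not say who does the real-time review, so it cannot be attributed to those who positioned the scan. And an upward effect on the grade is plausible, not shown.

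**Conclusion.** The point holds in limited form. The cohort has known tumour throughout, and the only presence-or-absence measure behind the detection objective is neither masked nor locked. Sections 6.5.4 and 6.9.0 disagree on whether uptake is judged in real time. The grade can therefore be set or revised with location known, which may raise the reported rate.

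The documents do not allow the amount to be computed. What follows from them is 5 percentage points per patient, given one lesion each; the 75% to 90-95% example and the table rest on assumed inputs. The tempting reading that the rate is in fact inflated goes beyond the text. This is a cheap improvement to how the result can be interpreted, and it affects neither the sample size nor any test.

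**What to change.** **In 6.5.4**
1. In the batch session, the existing reader grades the de-identified scan #2 first, because its field does not point to the tumour. The reader marks the site of any abnormal uptake and locks the 1-5 grade before opening other imaging, pathology or IHC results.
2. Location is then opened for region-of-interest placement, SUV and tumour-to-muscle ratio, and a location-aware grade is recorded.
3. Report the locked rate (grade 4-5 at the known site) beside the location-aware rate, each with an exact 95% interval.
4. Cross-tabulate the locked grade with IHC category 0-3.
5. State that masking is partial, because the reader knows that every patient has tumour and the low-dose CT may show it. If the same reader did the real-time quality check, recall is a further limit.

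**In 6.9.0**

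Reconcile the text with 6.5.4 so that real-time review covers image quality and incidental findings only.

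**Cost**

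Protocol wording and a few minutes per scan. The locked rate may be lower than the rate that would otherwise be reported. Nothing is lost, since both grades appear, and the number of patients and the imaging procedures do not change.

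### Nothing stops PET values and CCR2 IHC scores being set with the other known, and the power statement does not say which PET metric or scan it covers

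*Combined protocol and SAP*

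**What the plan says.** **The comparison.** Section 6.2.0 sets out to correlate tumour uptake "with immunohistochemical staining for CCR2 receptors in the tumor specimens", and objective 6.2.2 repeats this for CCR2 and other chemokine receptors. Section 6.7.0 says the association of uptake with "tissue signal intensity for CCR2 and other chemokine receptors will be evaluated using a Spearman correlation coefficient". It adds that 20 patients "achieves 80% power to detect a correlation of 0.61 using a two-sided hypothesis test" at the 0.05 level. The same section calls the study primarily descriptive, bases the sample size on feasibility, and gives image quality and CCR2 detectability as the primary goal.

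**The PET side.** Section 6.5.4 lists SUV and "tumor-to-normal tissue ratio (T/N) or tumor-muscle-ratio (T/M"), then distribution volume (DV) and binding potential (BP) from compartment models. It continues: "The graphical analysis using Logan and Patlak analysis to determine the volume of distribution (DV) also will be performed". A reference-region ratio (DVR) follows. The blood curve comes from a region "traced over the aorta (OR carotid artery"). On the reference tissue it says "A possible region of reference will be a suitably located" muscle in the field of view. It then commits to this: "All quantitative and semi-quantitative metrics of ^{64}Cu -DOTA-ECL1i-PET/CT will be correlated with CCR2 receptor expression and binding affinity of each biopsy-proven tumor specimen". Section 6.5.3.1 provides two acquisitions: a 60-minute dynamic scan and a limited scan 1-3 hours after injection.

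**The tissue side.** Section 6.5.9 has the study pathologist grade CCR2 from 0 to 3 on an overall assessment of all positively stained cells.

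**Timing.** Section 6.5.4 puts PET analysis in batches or after full enrolment, apart from a qualitative look for incidental findings. Section 6.5.9 puts tumour testing in batches or at the end of recruitment. Section 6.9.0 has an initial real-time review of quality and uptake, and CCR2 pathology after enrolment. Section 6.12.0 leaves the Image Analysis Form to the principal investigator's schedule.

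**The concern.** Both variables in the correlation involve judgement. On the PET side, the choice of ratio, input vessel and reference region is open. On the tissue side, one reader gives a global four-level grade. If either is settled with the other in view, the correlation can drift upwards without anyone intending it, and the report could not show that it had not.

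The second issue is interpretation. One power figure is attached to a quantity called uptake that could be any of several metrics from either of two scans. A reader of the results cannot tell which correlation the figure was meant to support, or how much weight to give whichever one is featured.

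**Working it through.** **1. Search for a lock or masking step.** Setting sections 6.5.3 to 6.5.4, 6.5.9, 6.7.0, 6.9.0 and 6.12.0 side by side:
- Section 6.5.4 says what PET readers may know (tumour location and all available imaging) but is silent on IHC.
- Section 6.5.9 describes the pathologist's score and is silent on PET.
- No section says which of the two analyses comes first.
- The real-time review in 6.9.0 would precede IHC, but it is only an initial review of quality and uptake. It does not fix SUV, ratio or kinetic values.

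**2. The plan's power figure.** Inputs from 6.7.0: n = 20, correlation 0.61, two-sided 0.05, Spearman. Using Fisher's z with the usual Spearman variance factor of 1.06:

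power = Φ(atanh(0.61) × √((20 − 3)/1.06) − 1.960) = Φ(0.7089 × 4.0047 − 1.960) = Φ(0.879) = 81.0%.

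Required n = 1.06 × ((1.960 + 0.842)/0.7089)² + 3 = 19.55, so 20. Simulation with untied data gives about 82%. The stated 80% is therefore right for one unadjusted test on untied data.

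**3. The same test with the planned score.** Assume a Spearman correlation of 0.61 with underlying continuous expression, which is then cut into four grades. The documents give no grade frequencies, so the splits are assumptions (40,000 simulated trials):

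| Assumed share in grades 0/1/2/3 | Power |
|---|---|
| 25/25/25/25% | 78% |
| 10/20/30/40% | 76% |
| 5/10/25/60% | 68-69% |

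**4. How many metrics?** Spearman depends only on ranks, so DVR and BP = DVR − 1 count once. A wide reading of 6.5.4 gives SUV, one ratio, compartment DV, compartment BP, Logan, Patlak and DVR: seven, or eight if both ratios or both model DVs are kept. A narrow reading, taking uptake as the semi-quantitative measures only, gives two (SUV and one ratio) per scan.

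**5. Chance of at least one nominal p<0.05 with no true association.** n = 20, one tissue readout, critical |rho| = 0.444 (t with 18 df), the three splits above, 20,000 simulated trials per cell. Between-metric correlations are assumed because the documents give none.

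| Metrics | Corr. 0.95 | Corr. 0.7 | Corr. 0.5 |
|---|---|---|---|
| 1 | 5% | 5% | 5% |
| 2 | 7% | 9% | 9-10% |
| 7 | 11% | 20% | 24-25% |
| 8 | 11% | 21-22% | 27% |

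With one metric, the median |rho| is 0.16. With seven or eight, the median of the largest |rho| is 0.24-0.37. It exceeds the quoted 0.61 in only about 1.3-3.6% of trials, against about 0.5% for one metric.

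**The case against.** The strongest reply is that these error rates describe a decision the plan never makes. The study is descriptive, sized by feasibility, has no p<0.05 success rule, and the correlation is not its primary goal. Section 6.5.4 promises every correlation, not the largest. This stands. A reader might infer that type I error is inflated or that the best result will be picked out, and the documents support neither.

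Nor is the PET analysis as open as it may look. The compartment model is chosen by nested F-test, AIC and the Schwarz criterion. These use the PET data alone, so model choice is not at issue. Muscle is the only reference tissue named. The choice of vessel affects only the metrics that use a blood input. These points narrow the gap but do not close it, since the reference is only a possible one and neither the ratio nor the vessel is fixed.

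A reader might also take the timing statements as outright contradictions. Staining in batches with scoring after enrolment would satisfy both 6.5.9 and 6.9.0. Section 6.5.4 itself allows an early qualitative look, and 6.9.0 goes further only by including uptake. These are ambiguities to clarify.

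**Conclusion.** The point holds at minor to moderate priority. The firmer half is masking: as written, either side of the objective 6.2.2 comparison could be settled with the other known. The documents do not show that this will happen, and they give no basis for sizing the effect.

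The other half is that the power statement has no identified metric or scan. Its numerical consequence is modest: about 6-10% for two metrics and 11-27% for seven or eight, against 5% for one. Those ranges rest on an assumed metric count, assumed between-metric correlations of 0.5-0.95, and no true association.

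It would be wrong to say that the 80% is miscalculated; it reproduces at 81-82%. It applies to untied data, and the planned four-level score brings it to about 68-78% under the splits tried.

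**What to change.** 1. In 6.5.4 and 6.5.9, state that PET regions, grades and metrics are locked before IHC scores are released, batch by batch where needed. State also that PET analysts work without IHC results and that the pathologist scores without PET results. Disclose any cases already read otherwise.
2. In 6.7.0, name one PET metric from one scan time against the CCR2 IHC score as the comparison the power statement covers. The choice is the sponsor's, provided it is fixed before IHC is seen. Report all other metrics, other receptors and binding affinity as exploratory estimates with 95% confidence intervals.
3. In 6.7.0, say that the 80% is for untied data, and give the lower range for a four-level score with its assumptions.
4. Clarify the timing wording across 6.5.4, 6.5.9 and 6.9.0.

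The cost is protocol wording and one data-lock step, with no change to scanning, tissue collection or patients. The downside is that the other metrics carry no inferential claim and IHC scores must wait for the PET lock. The documents do not report enrolment status; for cases already read, disclosure is all that remains.
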